9.2.2 Exploratory Data Analysis (EDA)

Exploratory Data Analysis (EDA) techniques such as histograms, QQ-Plots, box-plots, scatterplots and basic descriptive (means, medians, IQR) will be used to assess the distribution of dependent measures. These will be used to identify the distribution of outcomes which in turn will be conductive to determining the appropriate analysis strategies. In addition, these techniques will also be used to explore the most informative transformations of the covariates, confounders and relevant predictors considered in the analysis. Extreme values will be determined and their removal from the analysis will be determined. Missing patterns and rates will be assessed. However, missing data for the primary outcome are unanticipated given the availability of inpatient medication administration records. If patterns and MAR and rates are <20%, complete case analysis will be considered. If rates are >20% multiple imputation techniques will be used to complete the data. All variables included in the analysis (outcome, covariates, predictors, confounders) as well as other auxiliary variables should be included in the imputation process. In addition, multicollinearity will be assessed using Pearson's correlation coefficient and Variance Inflation Factor (VIF) analysis. Predictors with VIF>10 will not be included in the multivariable models.

Potential selection bias will be investigated comparing demographics, confounders and relevant predictors by caffeine used and by days. Unbalanced distributions of confounders and relevant predictors will be determined with standardized differences (SD). Measures with SD>0.1 will be included in the multivariable models.

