3 STUDY DESIGN

This will be a single-center, triple-blinded, randomized controlled trial at the University of Michigan Health System, and approval has been obtained from the University Michigan Medical School IRB. The overall study flow is presented in the CONSORT⁴¹ Flow Diagram (Figure 2). As with our past studies, patients will be recruited at preoperative clinics, where informed consent will be obtained. Randomization methods will follow a stratified randomization model to match patients based on age and gender. Participants will be randomized with a 1:1 allocation ratio (placebo: caffeine) in a two-arm parallel design, and the randomization schedule and coding will be held by our hospital research pharmacy. Prepared intravenous piggyback solutions of 5% dextrose in water or caffeine citrate (200 mg caffeine) will be directly delivered to the operating room prior to the surgery of enrolled participants. The dose of 200 mg was chosen for two reasons: (1) this dose is in-line with similar clinical neurophysiology studies involving caffeine^{34,35,42,43} and (2) this has been the intraoperative dose used for safely preventing post-dural puncture/post-operative pain in surgical and obstetric patients. ^{22,29,32} In these studies, no significant side effects or adverse events were reported in relation to caffeine. This study will fulfill CONSORT guidelines⁴¹ for clinical trials as outlined in the following sections. Furthermore, this trial will be registered with www.clinicaltrials.gov prior to trial initiation, and all study team members will be certified in Good Clinical Practice as outlined by the NIH.

Assessment for **Enrollment** eligibility **Exclusions** Randomization Allocation Allocation to placebo (n=30) Allocation to caffeine (n=30) Analysis Analysis Anesthetic emergence time ◆ Anesthetic emergence time ◆ EEG power and connectivity · EEG power and connectivity ◆ Trail Making Test ◆ Trail Making Test · Postoperative opioid use Postoperative opioid use • Postoperative pain assessments · Postoperative pain assessments Delirium assessments · Delirium assessments Depression, anxiety scales • Depression, anxiety scales ◆ Affect questionnaire ◆ Affect questionnaire ◆ 30-day follow-up health survey ◆ 30-day follow-up health survey

Figure 2: Planned study flow diagram based on Consolidated Standards of Reporting Trials (CONSORT)

Planned study flow diagram based on Consolidated Standards of Reporting Trials (CONSORT).⁴¹ EEG = electroencephalogram

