5 STUDY TREATMENTS

5.1 Allocation to Treatment

Participants will be block randomized with a 1:1 allocation ratio (placebo: caffeine) in a two-arm parallel design, and the randomization schedule and coding will be held by our hospital research pharmacy. Prepared intravenous piggyback solutions of 5% dextrose in water (placebo) or caffeine citrate (200 mg caffeine) will be directly delivered to the operating room prior to the surgery of enrolled participants.

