9 DATA ANALYSIS/STATISTICAL METHODS

9.1 Sample Size Determination

Sample size and power analysis is based on opioid consumption data observed in 102 hysterectomy patients treated at the University of Michigan with patient heterogeneity with respect to CNS involvement in the pain processing summarized by the Fibromialgia Survey score (FM). Acute opioid responses on POD1 varied between 0.7 and 6.5 (mean OME) with the standard deviation varying 3-18, dependent on the tertile of the FM score. Based on these data we hypothesize that caffeine affecting the pain processing system can show a difference as large as 0.7 vs. 6.5 with standard deviations of 3 and 10, respectively. This will give us the power of 83%, with a sample size of 60, to detect the difference by a two-sided ttest with unequal variances. We note that the opioid consumption distribution is of exponential type and therefore sample means, while approximately normal are a rather crude summary of the difference in the OME distribution by group. We therefore consider the above calculation conservative. The expected reserves of power attained through the use of the appropriate longitudinal model (see Analysis of Primary Endpoint) will be used to lend more power to secondary regression and causal analyses involving explanatory variables and potential mediators. We expect a ~10% drop-out rate, and will continue recruitment until the full 71 patients have been recruited (after drop-out).

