9.2.3 Analysis of Primary Endpoint

A generalized linear mixed model will be the primary analytic tool with appropriate datadriven choice of the link function. Linear regression will be used for assessing cumulative opioid consumption through postoperative day three. A separate analysis will entail longitudinal modeling with repeated oral morphine equivalent (OME) measurements (i.e., we will analyze multiple points of the OME curve simultaneously). A Gaussian subjectspecific intercept term will be included to model between-subject differences and the associated correlation structure. The Time variable (main effect, baseline, PACU, POD1-3) will be used to model the pattern of the respective outcome variable (response) over time in the placebo group. The Group variable (an indicator of the caffeine group, main effect) is an indicator of whether the subject received the caffeine intervention. The Group by Time interaction term expresses the differences of caffeine vs. placebo as far as the pattern of response over time is concerned. Final results will be assessed based on the best model selected using Likelihood Ratio tests and Akaike Information Criteria (AIC). In addition to the model specified above, a models will be constructed a) containing the above group and time specification with the addition of demographic variables and b) containing (a) with the addition of intraoperative factors.

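### Covariates enter on a standardised difference above 0.1, which chance alone exceeds about 70% of the time at 30 per arm, and the base primary models do not name the stratification factors age and gender

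*Combined protocol and SAP*

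**What the plan says.** Section 9.2.2 compares patient characteristics between the caffeine groups by standardised difference and then states: "Measures with SD>0.1 will be included in the multivariable models". It gives no covariate list and no criterion of prognostic value. The only stated ground for leaving a variable out is collinearity: "Predictors with VIF>10 will not be included in the multivariable models".

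Section 3 says: "Randomization methods will follow a stratified randomization model to match patients based on age and gender". Section 5.1 says only: "Participants will be block randomized with a 1:1 allocation ratio (placebo: caffeine) in a two-arm parallel design". Section 6.2.1 likewise mentions block randomisation without strata.

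Section 9.2.3 gives two base analyses of opioid use. One is for the cumulative total: "Linear regression will be used for assessing cumulative opioid consumption through postoperative day three". The other is a longitudinal model with a subject intercept, time, group and their interaction. Neither names a covariate. Additional model (a) is described as "containing the above group and time specification with the addition of demographic variables", and model (b) adds intraoperative factors to (a). Neither set is listed.

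For continuous secondary endpoints, section 9.2.4 defaults to a t-test or Mann-Whitney test and allows modelling where appropriate. TMT and affect are defined as changes from baseline. Section 3 expects that some TMT baselines will not be obtained and falls back on final scores.

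**The concern.** In a randomised trial, a baseline difference between arms is chance by construction. A threshold well inside the chance range sorts covariates mainly by luck, whereas adjustment gains precision only from covariates that predict the outcome. The analyst also cannot say before unblinding which covariates the models will hold.

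Stratification makes age and gender less likely than other variables to look imbalanced, so an imbalance screen tends to pass over the two factors the design balanced. If they predict opioid use and are left out, the standard error ignores that balance. The interval is then too wide and the test conservative.

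The secondary endpoints have a related gap. Baseline TMT and affect scores are collected, but the default analysis uses them only by subtraction.

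**Working it through.** **Inputs.** Threshold 0.1 (9.2.2); 30 per arm (Figure 2; 60 patients in 9.1); 71 patients, taken as 36 and 35 (9.1); means 0.7 and 6.5, SDs 3 and 10, stated power 83% (9.1). Two-sided alpha of 0.05 is assumed, since the plan states none.

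**The plan's own figure.** SE = √(9/30 + 100/30) = 1.906; noncentrality = 5.8/1.906 = 3.04; Satterthwaite df = 34.2; power = 84.0%. This reproduces the stated 83% within rounding and confirms 30 per arm as the planning basis.

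**Chance of passing the screen.** Under randomisation the standardised difference d is approximately normal with mean 0 and variance 1/n₁ + 1/n₂.
- 30 vs 30: SE = √(2/30) = 0.258; P(|d| > 0.1) = 2[1 − Φ(0.387)] = 69.9%. Simulation gives 70.1%.
- 36 vs 35: SE = 0.237; P = 67.4%.
- Binary covariates, exact, 30 per arm: 65% to 78% for prevalences from 10% to 50%.
- The threshold that chance passes only 5% of the time at 30 per arm is 1.96 × 0.258 = 0.51. For 0.1 to be that threshold would need 2 × (1.96/0.1)² ≈ 770 per arm.

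**Age and gender.** Assumed: 60 patients, blocks of 4 within two age bands by gender, age uniform from 20 to 80 split at 50, genders equal. Averaged over the two factors, the screen is passed in about 28% of trials. A check run of 5,000 trials splits this into about 48% for age, taken as continuous, and about 8% for gender.

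**Leaving age and gender out.** Same design, joint R² of 5% and 10% (assumed): the interval is 2% and 5% too wide, and type I error is 4.5% and 4.1%.

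**Rule against fixed age and gender.** Interval width relative to no adjustment at 60 patients, taking 0.1 or less to mean omission (an assumption):

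| Other candidates (assumed) | Age and gender R² (assumed) | Rule | Age and gender fixed |
|---|---|---|---|
| 8, not prognostic | 0 | 1.080 | 1.004 |
| 8, not prognostic | 10% | 1.063 | 0.951 |
| 4, not prognostic | 2.5% | 1.035 | 0.991 |
| 2, not prognostic | 2.5% | 1.017 | 0.991 |
| 4, joint R² 30% | 2.5% | 0.921 | 0.991 |
| 2, joint R² 30% | 2.5% | 0.902 | 0.991 |

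In the last two rows the rule is the narrower, by up to about 9% (0.902/0.991 = 0.910), with type I error of about 3.5% to 4.4%. No bias appeared beyond simulation error.

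**Baseline adjustment.** With correlation r and postoperative SD equal to k times the baseline SD, the variance ratio of baseline-adjusted to change-score analysis is k²(1 − r²)/(1 + k² − 2rk). Both r and k are assumed. Variance reductions at r = 0.3, 0.5, 0.7:
- k = 1: 35%, 25%, 15%
- k = 1.25: 22%, 11%, 2%
- k = 1.5: 13%, 4%, 0.2%

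**The case against.** **Reach.** The rule stands under exploratory analysis and speaks of multivariable models. It can naturally be read as governing only additional models (a) and (b), and model (a) may well include age and gender. This stands: a reader might infer that the rule sets the base primary model, or that measures at or below 0.1 are excluded, and the text says neither. The widths given for the rule depend on that unstated omission. The ambiguity is still a defect, because two analysts could fit different models from the same text.

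**Harm.** A reader might infer that the rule biases the estimate or raises the false-positive rate. For baseline covariates it does neither. Nor is there a general precision gain from dropping it. The rule's penalty is about 8% with eight non-prognostic candidates but under 2% with two, and the sign reverses if a few other covariates are strongly prognostic.

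**Prognostic strength.** Section 9.1 reports: "Acute opioid responses on POD1 varied between 0.7 and 6.5 (mean OME) with the standard deviation varying 3-18". One might use these figures to gauge how strongly age and gender predict opioid use. They describe tertiles of a fibromyalgia score in hysterectomy patients and say nothing about either factor, so every R² here is an assumption.

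**Secondary endpoints.** A t-test on change is valid under randomisation, and 9.2.4 permits modelling. This stands. The gain from baseline adjustment may be small if the postoperative scores are more variable than the baseline scores.

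**Conclusion.** The point holds and should be acted on, on grounds of prespecification and use of the design's strata. The figures of 70% (30 per arm) and 67% (71 patients) need only randomisation and a covariate not balanced by design. That the rule tends to pass over age and gender rests on the assumed strata and block size. The loss from omitting them is modest and in the conservative direction, and it arises only if they are prognostic.

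A reader might also infer that the fix makes the primary analysis correctly calibrated. It fixes the covariates in advance and no more: the data-driven link and the model selection by likelihood ratio tests and AIC in 9.2.3 are separate issues.

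**What to change.** 1. **Section 9.2.2:** replace the sentence on the 0.1 threshold with a statement that standardised differences are reported as description only and do not decide which covariates are included.
2. **Section 9.2.3:** include age and gender as fixed covariates in the model that gives the primary result, and say which model that is. Name in advance any further covariates, chosen for expected prognostic value and measured before the infusion. Reconcile section 3 (stratified) with sections 5.1 and 6.2.1 (blocks only).
3. **Section 9.2.4:** analyse postoperative TMT and affect scores with the baseline score as covariate. State one method for missing TMT baselines, for example the overall baseline mean plus a missing indicator. Say that it replaces the final-score fallback in section 3 and, for this covariate, the missing-data rule in 9.2.2, which includes "If rates are >20% multiple imputation techniques will be used to complete the data".

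**Cost.** Wording only, since the variables are already collected. If age and gender are not prognostic, naming them widens the interval by about 0.4% at 60 patients (0.3% at 71). Two further non-prognostic covariates bring this to 2.3% (1.9%). If strongly prognostic covariates (assumed joint R² of 30%) are left off the fixed list, the precision forgone is the reversal shown in the working, up to about 9%; a well-chosen list limits it.

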9.2.3 Analysis of Primary Endpoint

A generalized linear mixed model will be the primary analytic tool with appropriate datadriven choice of the link function. Linear regression will be used for assessing cumulative opioid consumption through postoperative day three. A separate analysis will entail longitudinal modeling with repeated oral morphine equivalent (OME) measurements (i.e., we will analyze multiple points of the OME curve simultaneously). A Gaussian subjectspecific intercept term will be included to model between-subject differences and the associated correlation structure. The Time variable (main effect, baseline, PACU, POD1-3) will be used to model the pattern of the respective outcome variable (response) over time in the placebo group. The Group variable (an indicator of the caffeine group, main effect) is an indicator of whether the subject received the caffeine intervention. The Group by Time interaction term expresses the differences of caffeine vs. placebo as far as the pattern of response over time is concerned. Final results will be assessed based on the best model selected using Likelihood Ratio tests and Akaike Information Criteria (AIC). In addition to the model specified above, a models will be constructed a) containing the above group and time specification with the addition of demographic variables and b) containing (a) with the addition of intraoperative factors.

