Variables: Postoperative opioid consumption, postoperative pain scores, time to anesthetic emergence, new sleep disturbances, electroencephalographic markers of brain recovery, postoperative cognitive function testing, depression/anxiety/affect scores, and perioperative caffeine use.

Statistical Methods: The analysis will be longitudinal with repeated oral morphine equivalent (OME) measurements i.e. we will analyze multiple points of the OME curve simultaneously. A generalized linear mixed model will be the primary analytic tool with appropriate data-driven choice of the link function. Power calculations reveal >80% power to detect difference by a two-sided t-test with unequal variances.

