Pain and sleep assessments: Inpatient opioid consumption will be monitored from the first PACU assessment through postoperative day three (or discharge, whichever occurs sooner) (primary outcome). Subacute opioid consumption (postoperative days 4-7) will be calculated as an additional outcome. All opioids will be converted to oral morphine equivalents (mg), and intraoperative opioid administration will be calculated as well and compared between groups. Pain measures will include the 10 centimeter Visual Analog Scale (VAS)⁴⁴ and Behavioral Pain Scale (BPS)⁴⁵ for subjective and objective pain assessment, respectively. Assessments will begin 1 hour after caffeine infusion has finished (once patient is in the PACU), and they will continue twice daily (morning and afternoon) for the first three postoperative days. Preoperatively, the Richards-Campbell Sleep Questionnaire (RCSQ)⁴⁶ will be administered to determine self-reported sleep quality the previous evening. As an additional outcome, self-reported sleep disturbances will also be assessed during these daily pain assessments (i.e., from the PACU through postoperative day 3).

EEG data acquisition: Our research group has extensive experience with EEG data acquisition and analysis in human volunteers^{47,48} and surgical patients.^{49,50} We have

demonstrated feasibility with collecting whole-scalp, 16-channel wireless EEG data (Cognionics, Inc.) in 50 surgical patients. Representative spectral and connectivity data are presented in Figure 3. Our group will use this same EEG technology to collect and analyze data for the proposed study. Spectral power (decibels, DB) and connectivity (phase lag index, PLI) data will be collected and analyzed during anesthetic emergence and PACU arrival.

[figure not shown]

Figure 3: Representative wireless EEG data from a surgical patient

Example wireless perioperative EEG data obtained from a related study (R01GM098578). LOC = loss of consciousness, PACU = postanesthesia care unit, dB = decibels, PLI = phase lag index (an EEG measure of functional connectivity).

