4.1.2 Exclusion Criteria

- 1. Emergency surgery
- 2. Severe cognitive impairment precluding capacity for informed consent
- 3. Uncontrolled cardiac arrhythmias
- 4. Seizure disorder history
- 5. Intolerance or allergy to caffeine
- 6. Preoperative opioid use
- 7. Pheochromocytoma
- 8. Enrolled in conflicting research study
- 9. Patients in acute liver failure
- 10. Pregnancy
- 11. Breastfeeding
- 12. Severe audiovisual impairment
- 13. Non-English speaking

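### The longitudinal OME model names a random intercept as its only correlation term and lists a baseline level that OME cannot inform, so its time-specific standard errors can be wrong in either direction

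*Combined protocol and SAP*

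**What the plan says.** Section 9.2.3 plans two analyses of opioid consumption. Cumulative consumption through postoperative day 3 is analysed by linear regression. A separate analysis models repeated OME values over time.

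For the repeated model, the correlation is handled as follows: "A Gaussian subjectspecific intercept term will be included to model between-subject differences and the associated correlation structure". The time factor is "The Time variable (main effect, baseline, PACU, POD1-3) will be used to model the pattern of the respective outcome variable". Group and Group by Time complete the fixed effects. No random slope, time-specific variance, residual covariance structure or robust standard error is mentioned.

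Two elements are left open. The section begins "A generalized linear mixed model will be the primary analytic tool with appropriate datadriven choice of the link function", so the link is not fixed. It also says "Final results will be assessed based on the best model selected using Likelihood Ratio tests and Akaike Information Criteria (AIC", without listing the candidate models.

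Three other passages bear on the point:
- Section 4.1.2 lists "Preoperative opioid use" as an exclusion.
- Section 3 says "Inpatient opioid consumption will be monitored from the first PACU assessment through postoperative day three".
- The Synopsis (Statistical Methods) says only that "we will analyze multiple points of the OME curve simultaneously". Neither it nor section 9.2.3 says whether the curve is a running total or consumption per interval.

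**The concern.** On an identity link, a random intercept implies the same variance at every time and the same correlation between every pair of times. OME is unlikely to meet either condition. Section 9.1 describes opioid consumption as exponential in type, so its spread rises with its mean, and it cites standard deviations from 3 to 18. If the response is a running total, variance also accumulates from PACU to POD3.

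The baseline level adds to this. With no preoperative users and counting from PACU, a baseline OME is either undefined or zero for everyone. A column of zeros pulls the pooled variance down and carries no information about treatment.

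At stake are the Group by Time test and the caffeine–placebo contrasts at each time, which might not hold their nominal 5% level. Section 9.1 also counts on extra power from the longitudinal model for secondary and mediator analyses, and section 9.2.4 allows similar modelling of secondary endpoints.

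**Working it through.** **Plan's own figure.** The only operating characteristic stated is 83% power (section 9.1). With 30 per arm, means 0.7 and 6.5, SDs 3 and 10, and two-sided alpha 0.05 (assumed), SE = √(9/30 + 100/30) = 1.906. The noncentrality is 5.8/1.906 = 3.04, Satterthwaite df are 34.2, and power is 84.0%. The figure reproduces and does not depend on the longitudinal model. The plan states no type I error for that model.

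**Closed form.** With balanced data and saturated Group by Time, the random-intercept model uses the average of the time-specific variances, v̄, at every time. The false-positive rate of the contrast at time t is then about 2·[1 − Φ(1.96·√(v̄/v_t))]. Levels are baseline, PACU, POD1, POD2, POD3, with baseline variance 0.

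- *Cumulative, independent equal increments:* variances 0, 1, 2, 3, 4; v̄ = 2; v_POD3 = 4. Rate 16.6%. Without baseline, v̄ = 2.5 and the rate is 12.1%.
- *Cumulative, with an equal shared patient component* (k + k²): 0, 2, 6, 12, 20; v̄ = 8; v_POD3 = 20. Rate 21.5%. Without baseline, v̄ = 10 and the rate is 16.6%.
- *Per interval, equal variances:* 0, 1, 1, 1, 1; v̄ = 0.8. Rate 8.0% at each postoperative time.
- *Per interval, falling use*, means 8, 6.5, 4, 2 (assumed) and variance proportional to the squared mean: 0, 64, 42.25, 16, 4; v̄ = 126.25/5 = 25.25. PACU: 1.96·√(25.25/64) = 1.23, rate about 22%. POD3: 1.96·√(25.25/4) = 4.92, rate about 0%.

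**Simulation under no drug effect.** 30 per arm, exponential OME with a gamma patient effect at two strengths, identity link, 6,000 trials per row. Mean profiles for PACU and POD1–3 are assumptions: flat 6, 6, 6, 6; falling 8, 6.5, 4, 2; POD1 peak 3, 6.5, 5, 4. Rejection of the POD3 contrast at nominal 5%:

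| Response, profile | Random intercept, baseline kept | Random intercept, baseline dropped | POD3's own variance |
|---|---|---|---|
| Cumulative, flat | 21.0–21.3% | 16.0–16.4% | 4.3–4.7% |
| Cumulative, falling | 14.3–14.4% | 10.0–10.3% | 4.2–4.8% |
| Cumulative, POD1 peak | 21.3–22.0% | 16.2–16.4% | 4.0–4.8% |
| Per interval, flat | 8.1–8.4% | 4.9–5.2% | 4.4% |
| Per interval, falling | 0% | 0% | 3.7–4.1% |
| Per interval, POD1 peak | 4.2–4.7% | 2.2–2.6% | 4.0–4.5% |

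A separate set of runs on the cumulative scale gave 21%, 19% and 15% for flat, peaked and falling use, so about 15–21% is a fair summary. Group by Time rejected about 10% on the cumulative scale and about 5–7% per interval. Per interval with falling use, the excess sits at PACU (20–24% across runs).

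**Reading.** On the cumulative scale the main driver is unequal variance over time; the baseline level adds about 4–6 points at POD3. Dropping baseline alone is enough only when interval variances are equal.

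**The case against.** The strongest reply is that the primary endpoint is one cumulative value per patient, analysed by linear regression, with the longitudinal model called separate. That stands: the regression has no repeated measures and this defect cannot reach it. A reader might infer that the trial's primary test runs at a 20% error rate, and the documents do not support that. The opening sentence of section 9.2.3 and the Synopsis do call the mixed model the main tool, but which analysis is primary is a different question.

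The link is also left to the data. With a gamma model and log link, variance follows the mean. A check with 1,000 null trials per interval, a POD1 peak and no baseline level gave 7.3% at POD1, 4.9% at POD3 and 6.7% for Group by Time. This stands for the per-interval case, although those data contained no zeros and suited the gamma model. On the cumulative scale the same kind of fit still gave 10–25% at POD3, with numerical warnings, and modelling log(1 + OME) gave 7–11%. A log link also has no finite estimate for an all-zero baseline level.

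The plan never states that baseline OME is zero; that is inferred. The time levels may be generic wording meant to serve outcomes with a real baseline, such as the Trail Making Test. This is plausible, and it is a reason to settle the wording for OME.

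Finally, selection by likelihood ratio and AIC might reach a better covariance. No covariance candidates are listed, so nothing commits the analyst to one.

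**Conclusion.** The point holds as a should-fix. A random intercept as the sole named correlation term does not suit OME on an identity link, and the baseline level is uninformative for this outcome. Time-specific standard errors are then wrong in both directions: contrasts reject too often where variance is above average and too rarely where it is below.

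The size depends on choices the plan leaves open. The 15–21% at POD3 requires a cumulative response and an identity link. Per interval, POD3 ranged from 0 to about 8% for flat, peaked or falling use, and reached 20–23% only if use rises over time. A reader might infer general inflation of about 20%, but the documents do not fix the response scale or link that would produce it. The simulated profiles and patient effect are assumptions, and the calculations take balanced, complete data.

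**What to change.** In section 9.2.3:

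1. Define the repeated response as OME per interval: PACU, POD1, POD2, POD3.
2. Remove baseline as a response level for OME. Keep it only for outcomes with a measured baseline.
3. Replace the random intercept as the sole correlation term with an unstructured covariance, fitted by REML with Kenward-Roger degrees of freedom. If a non-identity link is chosen, keep that link and use robust (sandwich) standard errors.

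With each time's own variance, the POD3 error rate in the scenarios above was about 4–5%.

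The cost is small. With four times, an unstructured covariance has 4 × 5 / 2 = 10 parameters against 2 for the random intercept, so 8 more to estimate from about 60 patients. Otherwise the change is a few sentences of plan text and a few lines of code. The linear regression of cumulative OME through POD3 needs no change on this account.

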2.2 Endpoints

2.2.1 Primary Endpoint

Cumulative opioid consumption (mg) through postoperative day 3 (or discharge, whichever is sooner.

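### The synopsis and 9.2.3 conflict on which analysis and contrast decide cumulative opioid use through POD3, and 9.2.2 allows extreme values to be removed without a rule

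*Combined protocol and SAP*

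**What the plan says.** Section 2.2.1 fixes the endpoint: "Cumulative opioid consumption (mg) through postoperative day 3", or discharge if sooner. Four statements then bear on its analysis.

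- Synopsis, Statistical Methods: "The analysis will be longitudinal with repeated oral morphine equivalent (OME) measurements", and "A generalized linear mixed model will be the primary analytic tool with appropriate data-driven choice of the link function". Linear regression is not mentioned.
- Section 9.1 refers to "The expected reserves of power attained through the use of the appropriate longitudinal model (see Analysis of Primary Endpoint", so it too treats a longitudinal model as the analysis of the primary endpoint.
- Section 9.2.3 repeats that the mixed model is the primary tool. It continues: "Linear regression will be used for assessing cumulative opioid consumption through postoperative day three". The next sentence begins: "A separate analysis will entail longitudinal modeling with repeated oral morphine equivalent (OME) measurements".
- After describing Time, Group and Group-by-Time terms, 9.2.3 adds: "Final results will be assessed based on the best model selected using Likelihood Ratio tests and Akaike Information Criteria (AIC". Two models with further covariates follow.

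The candidate models are not listed, no deciding contrast is named, and no alpha is given.

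Section 9.2.2 lets inspection of the outcome distributions guide the analysis strategy. It says that extreme values, and whether to remove them, will be determined at that stage. It gives no cut-off and does not require the decision to be blind to arm. Section 9.1 describes opioid consumption as having an exponential-type distribution.

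**The concern.** A reader of the final report could not tell from the plan which test was meant to decide the trial. Model selection is harmless to the error rate if it leaves the tested contrast alone. It is not harmless if it decides which treatment term is tested, because the trial then has two routes to a positive result. The text allows both.

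Extreme values raise a similar problem. With a right-skewed outcome, large values are expected real data and tend to sit in the arm that uses more opioid. Removing them can shrink the difference the trial is meant to estimate, and deciding on removal once results are visible adds another route to significance.

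**Working it through.** **1. The plan's own power figure.** Inputs from 9.1: means 0.7 and 6.5, SDs 3 and 10, total 60 (30 per arm), two-sided unequal-variance t-test, stated power 83%.

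- Standard error = √(3²/30 + 10²/30) = √(109/30) = 1.906
- Noncentrality = 5.8/1.906 = 3.04; Satterthwaite df = 34.2
- Power = 84.0% at alpha 5%, 62.5% at 1%, 90.9% at 10%

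Only 5% comes close to 83%, so two-sided 5% is assumed below. These inputs are for POD1 ("Acute opioid responses on POD1 varied between 0.7 and 6.5 (mean OME"), not for cumulative use.

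**2. Error rate by decision rule, asymptotic.** Assume balanced data and no effect. The average Group effect is then independent of the interaction statistic Q, which is chi-squared with k df: k = 3 for PACU and POD1-3, k = 4 if the listed baseline level is included. AIC prefers the interaction model when Q > 2k, with probability P = 0.112 (k = 3) or 0.092 (k = 4). The 5% critical values, 7.81 and 9.49, exceed 2k (6 and 8), so every significant interaction is also selected.

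- AIC selects, then Group or Group-by-Time is tested: 0.05(1 − P) + 0.05 = 9.4% (k = 3) and 9.5% (k = 4).
- As above, but with a joint test of both terms when the interaction model wins: 8.4% and 8.6%.
- LRT at 5% selects: 0.95 × 0.05 + 0.05 = 9.75%.
- One Group contrast always tested: 5%.

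**3. The same rules by simulation.** Random-intercept model fitted by maximum likelihood, 30 per arm, complete data, Gaussian and two skewed outcome shapes, 40,000 null trials per case.

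| Decision rule | False positives |
|---|---|
| Linear regression of the cumulative total, or Group always tested | 4.2-5.2% |
| AIC chooses; Group or Group-by-Time tested | 8.5-10.1% |
| AIC chooses; joint test if interaction wins | 7.5-9.2% |
| LRT chooses | 8.8-10.4% |
| AIC chooses; Group at the first time point read if interaction wins | 5.5-6.1% |

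In balanced data the first row's two tests coincide. At 35 per arm the second row is 8.8-9.9%. A separate simulation over 24 settings (30 or 36 per arm, 4 or 5 time points, intraclass correlation 0.3 to 0.7) gave 8.5-10.1% when AIC chose and any treatment term in the chosen model counted, and 3.9-5.2% with one fixed contrast.

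**4. Extreme values.** The plan gives no cut-off, so three are assumed, each computed over both arms pooled: Q3 + 1.5 IQR, Q3 + 3 IQR, and mean + 3 SD.

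- Size of the difference: with gamma data at the 9.1 means and SDs, the 5.8 difference becomes 1.9, 2.7 and 4.2. Under the first rule about 7.4 of 30 values are dropped in the higher-use arm and 0.7 in the lower-use arm.
- False positives with no effect: about 5% when all values are kept or one pooled rule is fixed in advance; about 5-8%, depending on skew and cut-off, when the choice to keep or remove follows sight of both results. On simulated cumulative totals, the best of four options (keep all, or one of the three cut-offs) gave 7.2-8.7%.

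**The case against.** The strongest reply is that 9.2.3 does assign an analysis to the primary endpoint. Linear regression is named for cumulative use, the longitudinal model is called separate, and the LRT/AIC sentence follows the description of that longitudinal model and may govern it alone. On that reading the error rate is about 5%. This stands as a reasonable reading, and it rules out saying that the plan assigns no analysis to the endpoint. It does not settle the matter: the same paragraph makes the mixed model primary and takes final results from the selected model, and the synopsis omits linear regression altogether.

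A reader might also infer that the trial's false-positive rate is 8-10%. The documents do not support that unconditionally. It requires LRT/AIC to choose among treatment terms and the chosen term to decide; the plan says neither. The simulations also use a Gaussian model with complete data, whereas the plan has a data-driven link and follow-up that may end at discharge. Because preoperative opioid use is an exclusion, baseline use would be near zero; fixing it at zero lowers the AIC rate to 7.9-8.6%, still above 5%.

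On extreme values, 9.2.2 does not commit to removal. A reader might imagine cut-offs set separately within each arm, which inflate error more, but no passage proposes them, so they are not evidence here. The shrinkage figures use POD1 inputs and do not estimate the effect on cumulative use. Research staff are blinded under section 3, but the plan does not say that this lasts through exploratory analysis.

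Finally, the synopsis gives feasibility as the primary objective of a Phase II trial. That lowers the stakes, but the plan still names an efficacy endpoint as primary and sizes the trial on opioid consumption.

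**Conclusion.** The point holds as a conflict in the text plus a missing rule. The synopsis and 9.2.3 do not agree on which analysis decides the primary endpoint, and no deciding contrast or alpha is stated. That conclusion needs no assumption.

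The size depends on how the conflict is resolved, with two-sided 5% assumed throughout. It is near 5% if linear regression with one Group coefficient decides. It is about 8-10% if LRT/AIC chooses the treatment term that is then tested, in a Gaussian random-intercept model with balanced data and about 30 per arm. Selection limited to link or covariates, with one contrast deciding, does not produce this inflation.

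The gap in 9.2.2 is separate. One pooled removal rule fixed in advance holds error near 5%; choosing after seeing both results gives about 5-8%. The fall from 5.8 to about 1.9-4.2 shows the direction and possible scale of the distortion on POD1 inputs, under assumed cut-offs and a gamma shape.

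**What to change.** In the synopsis and 9.2.3, name one primary analysis, one deciding contrast and a two-sided alpha. One option is linear regression of cumulative OME through POD3 with a single Group coefficient and covariates fixed in advance. If a longitudinal model is preferred, fix its link, its terms and one deciding contrast in advance. State that LRT/AIC selection applies only to supportive models.

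In 9.2.2, keep all values in the primary analysis except recording errors identified blind to arm, and make any outlier removal a sensitivity analysis.

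Unequal-variance standard errors, a rank-based sensitivity analysis and a definition of baseline OME are optional.

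The cost is wording in three places. If linear regression is primary, the trial gives up whatever extra power 9.1 expects from the longitudinal model. The stated 83% does not measure that loss, because it was calculated for POD1 means and not for either candidate analysis.
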